Study Objective	
Primary objective: This study is aimed at estimating the effectiveness of definitive radiotherapy as compared to standard surgical treatment for patients with primary sacral chordoma who are candidates to a complete en-bloc resection, in term of relapse-free-survival (RFS)
 
Secondary objectives: To estimate the efficacy, activity, safety, QoL of definitive radiotherapy as compared to standard surgical treatment for patients with primary sacral chordoma who are candidates to a complete en-bloc resection. To identify patients, radiological and pathological characteristics that might be used as predictors of relapse-free survival (RFS)/ progression free survival (PFS), overall survival (OS) To identify patients, radiological and pathological characteristics that might be used as predictors of treatment effects
 
Primary endpoint
 
 - The RFS, defined for each patient as the time from randomization (RCT) or treatment start date (PCS) to the date of local disease relapse, distant disease relapse, second primary malignancy or death from any cause, whichever occurred first. For patients treated with definitive radiotherapy not achieving CR as well as patients in R1/R2 after surgery not achieving a CR after post-operative radiotherapy the event for the RFS is the disease progression instead of the disease relapse. . 
Subjects not relapsed or died at the time of the analysis will be censored at the last disease assessment date. Disease relapse/progression will be determined radiologically for any appearance of new malignant lesion/s or dimensional increase of any size of malignant lesion/s already present at the baseline assessment.
 
Secondary endpoints
 
- Efficacy endpoints
 
 - Overall Survival (OS), defined for each patient as the time from randomization (RCT) or treatment start date (PCS) to the date of death from any cause. Subjects alive at the time of the analysis will be censored at the date of last contact. - Survival Post Progression (SPP), defined for each patient as the time from local disease relapse, distant disease relapse or second primary malignancy, whichever occurred first, to the date of death from any cause. SPP is equal to 0 in case of death before disease relapse. For patients treated with Radiotherapy not achieving CR as well as patients in R1/R2 after surgery not achieving a CR after Radiotherapy the starting point for the SPP is the local disease progression instead of the local disease relapse. 
- Activity endpoints
 
 - The Local Relapse Failure (LRF), defined for each patient as the time from randomization (RCT) or treatment start date (PCS) to the date of local disease relapse. Distant relapse, second primary malignancy or death before local disease relapse will be considered competing events; subjects alive and not relapsed at the time of the analysis will be censored at the last disease assessment date. Disease relapse will be determined radiologically for any appearance of new malignant lesion/s or dimensional increase of malignant lesion/s already present at the baseline assessment. For patients treated with Radiotherapy not achieving CR as well as patients in R1/R2 after surgery not achieving a CR after Radiotherapy the event for the LRF is the local disease progression instead of the local disease relapse.

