
SYNOPSIS

SACRAL Chordoma: a Randomized & Observational study on surgery versus definitive radiation therapy in primary localized disease (SACRO)

	
 - The Distant Relapse Failure (DRF), defined for each patient as the time from randomization (RCT) or treatment start date (PCS) to the date of distant disease relapse. Local relapse, second primary malignancy or death before any distant disease relapse will be considered competing events; subjects alive and not relapsed at the time of the analysis will be censored at the last disease assessment date. Disease relapse will be determined radiologically for any appearance of new malignant lesion/s or dimensional increase of malignant lesion/s already present at the baseline assessment. - Best Response rate to definitive radiotherapy will be evaluated radiologically at end of RT, 3 months, 6 months and 12 months after radiotherapy - Time to best response rate to definitive radiotherapy will be evaluated radiologically at end of RT, 3 months, 6 months and 12 months after radiotherapy. 
- Safety endpoints
 
 - Incidence, nature, severity and seriousness of AEs, according to NCI-CTCAE, version 4.0 (see Appendix 2) - Maximum toxicity grade experienced by each patient for each specific toxicity - Percentage of patients experiencing grade 3-4 toxicity for each specific toxicity - Patients with at least a SAE - Patients with at least a suspect unexpected serious adverse reaction (SUSAR) - Adverse events will be evaluated using the NCI-CTCAE scale, version 4.0 - Post-operative morbidity evaluated according to Clavien-Dindo scale - Neurological impairment evaluated according to CTC-AE scale (version 4.0) - 
- Quality of life (QoL) endpoints
 
 - Maximum grade experienced by each patient for each specific item - Maximum grade experienced by each patient for each specific dimension associated with QoL (e.g. functional ability, emotional well-being, sexuality/intimacy, family well-being, treatment satisfaction, and social functioning) - Average grade experienced by each patient for each specific item - Average grade experienced by each patient for each specific dimension associated with QoL (e.g. functional ability, emotional well-being, sexuality/intimacy, family well-being, treatment satisfaction, and social functioning) 
Quality of Life will be assessed through validated evaluation scale

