Disease Study	Localized sacral chordoma
Target Population	Patients with a primary and localized sacral chordoma amenable to complete surgical resection and definitive radiotherapy.
Sample Size	
All patients who met the enrollment criteria will constitute the study population that will be splitted in two cohorts according to the choice of each patient. The PCS population will include all patients, who refused randomization and started A. or B. treatment options. The RCT population will include all the enrolled patients who agreed to randomization and were randomized in the RCT study.
 
The safety-QoL population will include all the enrolled patients in both cohort who received option A or B.
 
Recruitment into the RCT will continue until the estimates have become sufficiently stable or extreme to allow a clinical decision in most patients, as indicated by the increasing rate of refusals to accept randomization; recruitment into the PCS will continue until new, more promising or less devastating therapies become available.

SYNOPSIS

SACRAL Chordoma: a Randomized & Observational study on surgery versus definitive radiation therapy in primary localized disease (SACRO)

	The study will be closed when all the enrolled patients will have completed the study treatment; the database lock and the last and definitive statistical analysis will be done approximately one year after the last patient has been enrolled.
Treatments	Definitive radiotherapy (adron therapy, carbon ion radiotherapy or proton therapy) as compared to standard surgical treatment.
Inclusion Criteria	
 1. Histologically confirmed diagnosis (brachyury expression) of primary sacral chordoma, of any diameter and arising at any site from S1 to coccyx. 2. Age \geq 18 years 3. ECOG-performance status (PS) 0-2 (Appendix 5) 4. No previous antineoplastic therapy 5. Macroscopic tumor detectable at MRI/CT scan 6. Patient amenable for surgery 7. Patient amenable for RT

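### Closing the study at end of treatment and locking about a year after an unspecified last patient does not fit the 12-month post-radiotherapy scan or the follow-up that RFS, OS, LRF and DRF need

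*Protocol*

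**What the plan says.** Four statements in the protocol synopsis bear on when the data are read.

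- **Closure** (Sample Size): "The study will be closed when all the enrolled patients will have completed the study treatment".
- **Lock** (Sample Size, next clause): "the database lock and the last and definitive statistical analysis will be done approximately one year after the last patient has been enrolled".
- **Recruitment ends** (Sample Size): for the RCT, "Recruitment into the RCT will continue until the estimates have become sufficiently stable or extreme to allow a clinical decision in most patients"; for the PCS, "recruitment into the PCS will continue until new, more promising or less devastating therapies become available".
- **Response schedule** (Study Objective, activity endpoints): "Best Response rate to definitive radiotherapy will be evaluated radiologically at end of RT, 3 months, 6 months and 12 months after radiotherapy".

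The primary endpoint, RFS, is "the time from randomization (RCT) or treatment start date (PCS) to the date of local disease relapse, distant disease relapse", among other events. Its censoring rule is: "Subjects not relapsed or died at the time of the analysis will be censored at the last disease assessment date". OS, LRF and DRF use the same starting points. The Statistical methods row plans two sequential analyses: the PCS first, as learning data, and the RCT second, as primary data. The Study Design row lets a site join the PCS alone.

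**The concern.** The lock is counted from enrolment, but the last response scan is counted from radiotherapy. Patients enrolled late cannot reach that scan before a lock set strictly at 12 months.

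Closure is tied to completion of treatment, although the primary endpoint and three secondary endpoints depend largely on what happens afterwards. Nothing in the synopsis says whether data are still collected between closure and lock.

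The lock also hangs on one patient whose cohort is not named, and neither cohort's recruitment has an operational stop. At stake are a scheduled assessment in late radiotherapy patients, the RFS follow-up of late recruits, and whether the time of the definitive RCT analysis can be known in advance.

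**Working it through.** The synopsis states no sample size, event count, power or precision target, so there is no such figure to reproduce. Its one relevant figure is the lock at about 12 months after the last enrolment. The interval from enrolment to end of radiotherapy, the accrual period and the RFS rate are not given and are assumed below.

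**1. Calendar.** Let d be the months from enrolment to end of radiotherapy. Assume 1-2 months to start and a 1-2 month course, so d = 2 to 4.

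- The 12-month scan falls at 12 + d = 14 to 16 months after enrolment, against a lock at 12. Any d > 0 gives a shortfall.
- The 6-month scan falls at 6 + d = 8 to 10 months and is in time, as are the two before it. One of the four assessments is lost.

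**2. Share affected.** With uniform accrual over A years, the share of radiotherapy patients enrolled in the last d months is d/(12A).

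- A = 5: 2/60 = 3.3% to 4/60 = 6.7%.
- A = 3: 2/36 = 5.6% to 4/36 = 11.1%.
- Widest range tried (d 1-6 months, A 2-10 years): 1/120 = 0.8% to 6/24 = 25%.

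**3. If data collection stopped at closure.** Suppose every patient takes the same d. A patient enrolled t months before the last one then ends radiotherapy t months before closure, and the scan due k months after radiotherapy is lost when t < k.

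- 12-month scan: 12/60 = 20% (A = 5) or 12/36 = 33% (A = 3).
- 6-month scan: 6/60 = 10% or 6/36 = 17%.
- 3-month scan: 3/60 = 5% or 3/36 = 8%.

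**4. Which last patient.**

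- *Last in either cohort.* RCT patients may be followed well beyond a year, but the definitive RCT analysis waits for PCS recruitment to end. That end has a condition but no date, number or measurable criterion.
- *Last in the RCT.* The analysis is anchored to the RCT, although the RCT stop is not quantified either. The last RCT patients have about one year of RFS follow-up.

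**5. RFS events at lock.** Assume exponential RFS with 5-year value S5, so the rate is λ = -ln(S5)/5 per year. With uniform accrual over A years and minimum follow-up F, the expected event fraction is 1 - [exp(-λF) - exp(-λ(A+F))]/(λA). For A = 5:

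| S5 | λ | F = 1 | F = 3 | F=3 / F=1 | F=1 / F=3 |
|---|---|---|---|---|---|
| 50% | 0.1386 | 37.2% | 52.4% | 1.41 | 71% |
| 70% | 0.0713 | 21.7% | 32.1% | 1.48 | 68% |

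A patient followed for exactly one year has an event probability of 1 - exp(-λ) = 12.9% (S5 = 50%) or 6.9% (S5 = 70%). Over A = 2-10 years and median RFS 3-10 years, the one-year lock keeps 53-86% of the events available at three years.

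**The case against.** Four points can fairly be made for the plan.

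- **Closure may be administrative.** The clause after it places lock and analysis later, and RFS censoring refers to the time of the analysis. Follow-up may therefore continue after closure. This stands as a possible reading, so step 3 is conditional. The synopsis does not say so, however, and the two clauses still need reconciling.
- **The loss at lock is small.** One of four scans is missed, for a secondary endpoint, in a small share of radiotherapy patients, and the lock time is only approximate. This limits the size. The approximation does not guarantee that the scan is included.
- **The two timing problems need different readings.** Short RCT follow-up and an RCT analysis waiting on the PCS cannot both hold in full. That is correct. Each reading has its own difficulty, and the text does not choose between them.
- **No target is missed.** The design estimates a posterior distribution, and the synopsis sets no event or precision goal. Fewer events mean less precision, not in themselves bias. The SAP, which is not at hand, may fix the PCS data cut.

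A reader might infer that most RFS information is lost, that the response endpoint is missing altogether for late patients, or that PCS recruitment never ends. The documents support none of these. Under the 5-year accrual assumed above, 68-71% of the three-year events are already present at one year. With d of 2 to 4 months, late patients keep three of four scans at a 12-month lock. PCS recruitment has a stated condition, though not an operational one. A suspicion that the analysis date would be chosen to suit the results is also speculative: the protocol openly lets accumulating estimates govern RCT recruitment.

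**Conclusion.** The point holds as an inconsistency within the protocol. Closure at end of treatment and a lock about 12 months after the last enrolment do not match a response schedule counted from radiotherapy or endpoints that need post-treatment follow-up. That much needs no assumed figure beyond d > 0.

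The loss at lock is modest: one scan in about 3-7% of radiotherapy patients with 5-year accrual or 6-11% with 3-year accrual, both for an assumed d of 2 to 4 months. It is larger only if collection stops at closure. The unspecified last patient leaves either the date of the definitive RCT analysis dependent on the PCS, or the last RCT patients with about a year of RFS follow-up.

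The RFS figures rest entirely on assumed accrual and event rates and do not show that a one-year lock is inadequate.

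**What to change.** Amend the Sample Size text in four places.

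1. Define end of study by the end of follow-up for the time-to-event endpoints, and state that data collection continues after treatment.
2. Start the lock clock for the primary analysis from the last RCT patient.
3. Lock no earlier than that patient's 12-month post-treatment scan plus a stated visit window. With d = 2 to 4 months this is 14 to 16 months after the last RCT enrolment, plus the window.
4. Set the cut-off for the PCS learning data before RCT outcomes are viewed. Because accumulating estimates steer RCT recruitment, the rule should be written in now.

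This takes protocol wording and no more patients. The downside is a final report some months later.

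A longer minimum RFS follow-up is an option for the sponsor, not a required correction. For example, three years instead of one would give 41-48% more events from the same patients under 5-year accrual and 5-year RFS of 50-70%, with the report about two years later.
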